Novartis will supply ofatumumab to the investigator as content-labeled Ofatumumab vials presented as either 100 mg – acetate formulation, 20 mg/mL, 5 mL fill vials, or 1000 mg – acetate formulation, 20 mg/mL, 50 mL fill vials. The investigational medical product, ofatumumab, is a liquid concentrate for solution for infusion presented in glass vials. Ofatumumab will be infused intravenously according to the study schema. The ofatumumab infusions will be prepared in 1000 mL NaCl sterile, pyrogen free 0.9% NaCl to yield the appropriate concentration per study dose level. Ofatumumab vials must be stored at 2-8°C. Protect from light and do not freeze. No special packaging components, other than the outer white cardboard carton in which the vials are placed, will be used to afford light protection.

Ofatumumab open-labeled product will be for intravenous infusion. The site is responsible for labeling individual vials for investigational use. All items required for administration of study medication (e.g., infusion bags, filters, etc.) are to be provided by the site.

Composition of Ofatumumab Injection 20 mg/mL

The quantitative composition of acetate formulation 20 mg/mL. This is available in two fill volumes, 5 mL / vial (100 mg/vial) and 50 mL/vial (1000 mg/vial).

Ingredient	Quantity/ mL
Ofatumumab	20.0 mg
Sodium Acetate, Trihydrate	6.80 mg
Edetate Disodium, Dihydrate (EDTA)	0.019 mg
Polysorbate 80	0.20 mg
L-Arginine	10.0 mg
Sodium Chloride	2.98 mg
Hydrochloric Acid	to give pH 5.5
Water for Injection	q.s. to 1.0 mL

Preparation of Ofatumumab Infusion

Ofatumumab will be prepared as 1000 mL dilution of ofatumumab in sterile, pyrogen-free 0.9% NaCl. The exact time of dilution into the 0.9% NaCl must be written on the label of the infusion bag.

Once diluted into saline, the product is stable for up to 24 hours at ambient temperature. The product must be discarded after 24 hours following preparation. However, the product contains no preservative and should be used as soon as possible after dilution.

Preparation of drug solution for intravenous injection by the site pharmacist or designee will be done in accordance with the protocol, and in these dilution instructions.

Ofatumumab intravenous solution will be prepared using standard dilution methods and following general aseptic practice standard to preparation of IV medications. Eyes and hands should be protected when handling ofatumumab.

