For intravenous administration, compatibility of the following components for ofatumumab in clinical studies (i.e., not for commercial product) has been established:

Dosing Components for Ofatumumab in Clinical Studies

Dosing component	Material of construction	Suggested Vendor
1L Saline Bags	Polyvinyl Chloride (PVC)	Baxter
	Polyolefin [polyethylene* (PE)/polypropylene (PP)]	Baxter, B. Braun
Administration Set	PVC	Baxter
	PVC lined with Polyethylene	B. Braun
Filter Extension Set	Sterilizing-grade (0.22 µm) hydrophilic filter	Durapore brand by Millipore
	Lines made of PVC, filter membrane material polyether sulfone	Baxter
	Lines made of PVC lined with Polyethylene, filter membrane material polyether sulfone	Alaris/Cardinal Health (Ref # 10010454)
1 Liter 0.9% Sodium Chloride	NDC #00338-0049-04	McKesson, Mck Item # 148-2538

Preparation of the 1000 mL infusion bags should be done on the day of planned infusion.

* polyethylene (IUPAC name: polyethene)

Materials for Preparation and Administration of Infusion

The following materials are needed when preparing and administering the infusion:

1000 mL sterile pyrogen free 0.9% saline (NaCl) infusion bag(s).

The solution can be kept at ambient temperature for a maximum of 48 hours after preparation; however, the product does not contain a preservative and dosing should begin as soon as possible after dose preparation.

Ofatumumab 100 mg and 1000 mg vials (supplied by Novartis)

Needles and syringes (50 mL sterile syringe) not supplied by Novartis

Intravenous (IV) cannula (not required if subject has central venous access) [not supplied by Novartis]

Infusion pump and infusion tubing set (not supplied by Novartis)

In-line low protein binding, polyether sulfone filter 0.2 μm (please make sure a spare filter is available in case the filter needs to be changed) [not supplied by Novartis].

Please note that the commercial filters are sterilizing-grade (0.22 μm) hydrophilic Durapore by Millipore.

Dilution of Ofatumumab

- Ensure the correct container number is used.
- Take a 1000 mL infusion bag (sterile pyrogen free 0.9% saline), remove and dispose of the appropriate amount of saline according to tables below.
- Draw the required amount of ofatumumab according to the table below (100 mg vials)
- Inject ofatumumab into the saline bag
- Invert the infusion bag slowly 3 times, avoiding formation of any foam
- Label the infusion bag with the completed label

Preparation of Ofatumumab Infusion: 100 mg vials

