Dose of Ofatumumab	Infusion bag size	Volume of NaCl to be removed from infusion bag	Volume ofatumumab (number of ofatumumab vials)
300 mg	1000 mL	15 mL	15 mL (3 vials, 5 mL/vial)
700 mg	1000 mL	35 mL	35 mL (7 vials, 5mL/vial)
1000 mg	1000 mL	50 mL	50 mL (10 vials, 5 mL/vial)

Ofatumumab Infusion Set up

Ofatumumab must be administered by i.v. infusion through an in-line filter and through a well-functioning i.v. catheter (i.v. cannula) into a vein in the arm (or other venous access) by an infusion pump.

Please Note: It is mandatory to use an in-line low protein binding 0.2 micron polyether sulfone filter for all IV dosing of ofatumumab drug product.

DO NOT ADMINISTER AS AN INTRAVENOUS PUSH OR BOLUS.

[figure not shown]
Ofatumumab should not be mixed with any other medication. If ofatumumab is to be dosed through an in-dwelling catheter, then, any previous medication should be removed by flushing with normal saline prior to dosing with ofatumumab.

Please note that the infusion site can be used for blood sampling only if there is no risk of contamination of the infusion needle with the saline, infusion solutions, or any other fluid(s). Only a newly inserted needle can be used for the predose blood samples.

- Check subject ID against the label on the infusion bag and ensure the expiry of the solution. The solution must be administered in its entirety to the subject within 24 hours from time of preparation.
- Attach the 1000mL infusion bag to the infusion set (if not done at the pharmacy).
- Attach the in-line filter to the infusion set (closest to the subject; see schematic below). **Note: The in-line filter must be used during the entire infusion.**
- Prime the infusion set and filter with ofatumumab (if not done at the pharmacy).
- In case of a problem with the filter (i.e. clogging/blockage), please change, re-prime the new filter, and continue the infusion.

- In case of problem with infusion set, follow local procedures.
- Collect the pre-dose blood samples, if required.
- Check the backflow from the i.v. cannula according to routine practice at site
- Set the pump at the initial infusion rate 12mL/hr for the first infusion and 25mL/hr for the subsequent infusions (see below infusion guidelines)

Infusion Set-Up Schematic

iii. Use of topical (non-systemic) therapies for chronic GVHD

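### Diluted ofatumumab may be kept 48 hours under one heading of Section IV.ii but only 24 hours under two others

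*Combined protocol and SAP*

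**What the plan says.** Three headings within Section IV.ii (Ofatumumab) of the combined protocol and SAP set a time limit on the diluted product.

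- *Preparation of Ofatumumab Infusion*: "Once diluted into saline, the product is stable for up to 24 hours at ambient temperature", followed by "The product must be discarded after 24 hours following preparation". It also requires that "The exact time of dilution into the 0.9% NaCl must be written on the label of the infusion bag".
- *Materials for Preparation and Administration of Infusion*: "The solution can be kept at ambient temperature for a maximum of 48 hours after preparation". The same sentence notes that there is no preservative and adds that "dosing should begin as soon as possible after dose preparation".
- *Ofatumumab Infusion Set up*: "The solution must be administered in its entirety to the subject within 24 hours from time of preparation". The same bullet has staff check the expiry of the solution before starting.

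Just before the Materials list, at the end of *Dosing Components for Ofatumumab in Clinical Studies*, there is a further instruction: "Preparation of the 1000 mL infusion bags should be done on the day of planned infusion".

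**The concern.** The Materials text doubles the limit given under the other two headings. Pharmacy or nursing staff who read only that text could keep, or go on using, a bag that the other headings require them to discard. The product has no preservative and the patients are immunosuppressed, so the in-use limit matters as a safety rule.

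The conflict bites in two situations: an infusion postponed after the bag has been made up, and one so prolonged by reactions that the bag passes 24 hours. The second is not far-fetched in principle. The dose-modification rules provide for slowing, interruption and a 12 mL/h restart after a grade 3 reaction, and Section VII anticipates overnight stays caused by slow infusion.

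The required label records when the bag was diluted. The text does not ask for a printed expiry time, so the bedside check depends on which limit staff apply.

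**Working it through.** **Can the limits be reconciled?** The three texts, side by side:

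| Heading in Section IV.ii | Limit | Clock starts | Condition stated |
|---|---|---|---|
| Preparation of Ofatumumab Infusion | 24 h, then discard | Preparation (dilution) | Ambient temperature |
| Materials for Preparation and Administration of Infusion | 48 h | Preparation | Ambient temperature |
| Ofatumumab Infusion Set up | 24 h to complete the dose | Preparation | None stated |

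- *Different storage condition?* No. The 48-hour text and the 24-hour stability text both specify ambient temperature.
- *Different clock?* No. All three count from preparation.
- *Different product?* No. *Composition of Ofatumumab Injection 20 mg/mL* describes one acetate formulation in two fill volumes, and neither limit is tied to a vial size or bag material.
- *Plain saline instead of drug?* No. The 48-hour sentence follows the saline-bag item, but its remarks on preservative and on dose preparation show that it means the made-up drug.
- *Storage against administration?* Only in part. The Set up limit concerns completing the dose, but the Preparation limit is itself a stability and discard rule, so keeping a bag for 48 hours breaks it directly.

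The difference is 48 − 24 = 24 hours. Any bag aged between 24 and 48 hours is subject to contrary instructions.

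**Would a bag reach that window?** Inputs are the 1000 mL bag volume and the two infusion-rate tables, which step every half hour.

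1. First infusion. Volume in the first 3 h = (12 + 25 + 50 + 100 + 200 + 300) × 0.5 = 343.5 mL. The remaining 656.5 mL at 400 mL/h takes 656.5 / 400 = 1.64 h. The total is about 4.6 h, matching the protocol's figure.
2. Second infusion. Volume in the first 2 h = (25 + 50 + 100 + 200) × 0.5 = 187.5 mL. The remaining 812.5 mL at 400 mL/h takes 812.5 / 400 = 2.03 h. The total is about 4 h, again matching.
3. Latest start for an uninterrupted first infusion to finish within 24 h: 24 − 4.64 ≈ 19.4 h after preparation.
4. Mean rate, pauses included, needed by a bag started at once: 1000 / 24 = 41.7 mL/h to finish within 24 h, and 1000 / 48 = 20.8 mL/h to finish within 48 h.
5. Held at 12 mL/h throughout, a full bag would take 1000 / 12 = 83.3 h and exceed both limits. The protocol lets the rate rise again if tolerated, so this is an extreme.

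A bag run on schedule and started promptly never reaches the disputed window. It gets there if the start is delayed beyond about 19 hours, or if the mean rate falls between about 20.8 and 41.7 mL/h. The documents give no basis for estimating how often either would happen.

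**The case against.** The strongest reply is that the working rule is already clear. The 48-hour wording is permissive and sits in a list of materials, whereas the two 24-hour rules are mandatory and sit in the procedural text. A permitted maximum does not override a mandatory one, and a site that observes 24 hours satisfies all three. Same-day preparation, the dilution time on the label and the expiry check beside the 24-hour deadline all make a breach unlikely.

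The prolonged-infusion scenario is also weaker than it looks. The 48-hour sentence most naturally concerns storage before dosing, and completion of a running infusion is governed by the Set up text. If, after a grade 3 reaction, the rate climbed again on the first-infusion table (an assumption), even a full bag would need only about 4.6 hours more. Passing 24 hours would then take roughly 19 hours of pause or failure to escalate. The Section VII remarks on overnight stays concern SAE classification and do not show a bag in use beyond 24 hours.

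Most of this stands, and it limits the weight of the point. The core conflict is over storage before the start, with prolonged infusion secondary. The reply does not remove the contradiction, however. Nothing in these headings says that the stricter limit prevails, and the same-day instruction refers to the planned infusion without saying what becomes of a bag when the plan slips.

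**Conclusion.** The inconsistency holds. One heading allows 48 hours from preparation where two require 24, and no text reconciles them. In practice it is minor: it affects only bags between 24 and 48 hours old, which the scheduled infusions do not produce when started promptly. No harm is demonstrated, and no endpoint, sample size, error rate or analysis is touched.

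The conclusion rests on reading all three limits as applying to the same diluted product, which the text supports. It does not rest on 24 hours being technically right. The documents give no stability data for either figure, so the case for 24 is that it is the more cautious limit and the one stated under two headings. Correction is worthwhile because this is a live handling instruction for a preservative-free infusion in immunosuppressed patients.

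**What to change.** In *Materials for Preparation and Administration of Infusion*, replace 48 hours with 24 hours. Add a cross-reference to *Preparation of Ofatumumab Infusion* and *Ofatumumab Infusion Set up*, so that the single rule is that the infusion is completed within 24 hours of preparation. Keep a longer limit only if the supplier confirms stability for that period and the other two headings are amended to match.

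The cost is one figure and one cross-reference. Dose, schedule, endpoints and analysis stay as they are.

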- For Grade 4 infusion reactions, do not resume the infusion (subjects who experience a grade 4 toxicity at least possibly due to ofatumumab will not receive further doses of ofatumumab).
- For Grade 1, 2, or 3 infusion reaction, if the infusion reaction resolves or remains less than or equal to Grade 2, resume infusion with the following modifications according to the initial Grade of the infusion reaction:

Grade 1 or 2: Infuse at one-half of the previous infusion rate.

Grade 3: Infuse at a rate of 12 mL/hour.

Thereafter, the infusion rate may be increased as tolerated.

Subsequent Infusions of Ofatumumab:

If the previous infusion has been completed without grade ≥ 3 infusion-associated AEs, the subsequent infusion of ofatumumab (300mg at 0.3 mg/mL; 700mg at 0.7mg/mL; and 1000mg at 1mg/mL) can start at a rate of 25 mL/hour and may be doubled approximately every 30 minutes up to a maximum of 400 mL/h, according to the following table. Duration of the infusion will be approximately 4 hours if this schedule is followed. If the previous infusion has been completed with grade ≥ 3 infusion-associated AEs, the subsequent infusion should start at a rate of 12 mL/hour. However, actual dose delivered (e.g. 300mg, 700mg or 1,000mg dose cohort level) will not be modified on day 14 dose.

Dose Modification for subsequent infusions of Ofatumumab:

- If an infusion reaction develops, the infusion should be temporarily slowed or interrupted.
- For Grade 4 infusion reactions, do not resume the infusion (subjects who experience a grade 4 toxicity at least possibly due to ofatumumab will not receive further doses of ofatumumab)
- For Grade 1, 2, or 3 infusion reaction, if the infusion reaction resolves or remains less than or equal to Grade 2, resume infusion with the following modifications according to the initial Grade of the infusion reaction:

Grade 1 or 2: Infuse at one-half of the previous infusion rate.

Grade 3: Infuse at a rate of 12 mL/hour.

Thereafter, the infusion rate may be increased as tolerated.

Infusion rate at subsequent ofatumumab infusion

Time	mL/hour
0 – 30 minutes	25
31 – 60 minutes	50
61 – 90 minutes	100
91 – 120 minutes	200
121+ minutes	400

*acceptable window surrounding each time frame for escalation of infusion rate is +/- 10 minutes.

During infusion the patient should be monitored closely and appropriate measurements should be performed whenever judged necessary.

Technical details of Ofatumumab composition and dosing:

Medication

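### Section IV.ii gives two different starting rates for the day 14 infusion after a grade 3 infusion event on day 0: 12 mL/h in the subsequent-infusion rule and 25 mL/h in the pump set-up step

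*Combined protocol and SAP*

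**What the plan says.** All the relevant text is in Section IV.ii (Ofatumumab) of the combined protocol and SAP. Ofatumumab is given twice, on days 0 and 14, so a subsequent infusion can only be the one on day 14.

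- **Subsequent Infusions of Ofatumumab.** This paragraph sets a conditional starting rate. "If the previous infusion has been completed without grade ≥ 3 infusion-associated AEs", the infusion "can start at a rate of 25 mL/hour and may be doubled approximately every 30 minutes up to a maximum of 400 mL/h". For the other case it says: "If the previous infusion has been completed with grade ≥ 3 infusion-associated AEs, the subsequent infusion should start at a rate of 12 mL/hour". It adds that the dose itself stays the same on day 14.
- **Rate tables.** The table for the first infusion starts at 12 mL/h and steps through 25, 50, 100, 200 and 300 to 400 mL/h. The other table, headed "Infusion rate at subsequent ofatumumab infusion", starts at 25 mL/h and steps through 50, 100 and 200 to 400 mL/h.
- **Dose modification bullets.** These end treatment after a grade 4 event: "subjects who experience a grade 4 toxicity at least possibly due to ofatumumab will not receive further doses of ofatumumab". After a grade 3 reaction the same infusion may be resumed, if the reaction has settled sufficiently, at 12 mL/h and then increased as tolerated.
- **Ofatumumab Infusion Set up.** The last step of the set-up list reads: "Set the pump at the initial infusion rate 12mL/hr for the first infusion and 25mL/hr for the subsequent infusions". It closes with a bracketed pointer, "see below infusion guidelines". What comes after it is the heading of a set-up schematic and then the part on topical therapies.

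**The concern.** The set-up list is the step-by-step instruction for the person programming the pump. It names a rate for every infusion after the first and does not mention the exception. Someone working from that list would start a day 14 infusion at 25 mL/h in a patient for whom the subsequent-infusion paragraph gives 12 mL/h.

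The group concerned is small but identifiable: patients with a grade 3 infusion event on day 0 who go on to day 14. The protocol treats infusion rate as a safety control. Section V.1 lists changing the rate among the ways infusional toxicity is managed, and the background describes how the rheumatoid arthritis study lengthened the infusion time, increased the volume and strengthened premedication after severe reactions. As the day 14 dose is not modified after a reaction, the starting rate is the setting that the subsequent-infusion paragraph changes for these patients, and on that setting the protocol gives two answers.

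**Working it through.** **Are both rates genuine schedule starts?** A typing error in one of them would show up in the stated durations. Each table step lasts 0.5 h, the bag holds 1000 mL, and the remainder runs at 400 mL/h:

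duration = 0.5 × (number of steps) + (1000 − volume given in the steps) / 400

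- First infusion: 0.5 × (12 + 25 + 50 + 100 + 200 + 300) = 343.5 mL in 3 h. Then (1000 − 343.5)/400 = 1.64 h. The total is 4.64 h; the protocol states about 4.6 h.
- Subsequent infusion: 0.5 × (25 + 50 + 100 + 200) = 187.5 mL in 2 h. Then (1000 − 187.5)/400 = 2.03 h. The total is 4.03 h; the protocol states about 4 h.

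Both figures reproduce, so 12 and 25 mL/h are the intended starts of two distinct schedules.

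**What does each instruction give for day 14?**

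| Worst infusion event on day 0 | Subsequent-infusion paragraph | Set-up step |
|---|---|---|
| None, or grade 1–2 | 25 mL/h | 25 mL/h |
| Grade 3 | 12 mL/h | 25 mL/h |
| Grade 4, at least possibly due to ofatumumab | No further dose (dose modification bullets) | Does not arise |

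Only the middle row conflicts.

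**How large is the difference?**

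- Ratio of starting rates: 25/12 = 2.08.
- Volume in the first 30 minutes: 0.5 × 25 = 12.5 mL against 0.5 × 12 = 6 mL.
- Drug in the first 30 minutes, at the concentrations in Section IV.ii: 3.75 against 1.8 mg (300 mg level, 0.3 mg/mL); 8.75 against 4.2 mg (700 mg level, 0.7 mg/mL); 12.5 against 6 mg (1000 mg level, 1 mg/mL).

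**Which table follows a 12 mL/h start on day 14?** The table that starts at 12 mL/h is headed for the first infusion, and the table for subsequent infusions has no 12 mL/h row. Two readings can be compared purely to size the gap. Using the first-infusion table gives 4.64 h, as above. Putting one 12 mL/h step in front of the subsequent-infusion table gives 0.5 × (12 + 25 + 50 + 100 + 200) = 193.5 mL in 2.5 h, then (1000 − 193.5)/400 = 2.02 h, so 4.52 h. The readings differ by 0.125 h, or 7.5 minutes, and in whether there is a 300 mL/h step. The gap is small, but the text does not close it.

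**The case against.** The strongest reply is that the subsequent-infusion paragraph is the full rule and covers both cases, while the set-up step is a one-line equipment instruction that defers to fuller guidance. Read together, the step is a default and the paragraph supplies the exception. That is a fair account of how a careful reader might resolve the conflict, and it limits its seriousness. It does not remove it. The step is worded for all subsequent infusions, and its pointer leads downwards when the rules and tables are above it. A figure may be missing under the schematic heading, so nothing here rests on that space looking empty; the point is where the rate rules actually stand.

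Three stronger readings are tempting, and the documents do not support them.

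- *A patient started at 12 mL/h on day 14 has no escalation sequence.* The first-infusion table prints one from that rate. What is missing is a statement of whether it applies on day 14.
- *Everyone with a grade 3 or higher event is exposed to the conflict.* The paragraph uses that wording, but the grade 4 rule leaves essentially the grade 3 patients.
- *The conflict distorts the dose-limiting toxicity count.* Section V.1 excludes grade 1–3 infusion events from that count. An effect would need a grade 3 event on day 0, staff following the set-up step over the paragraph, and then a grade 4 reaction on day 14 caused by the starting rate. The documents quantify none of these links. The nearest figures, from Part A of the rheumatoid arthritis study, put 74 of 79 infusion-day events (94%) on the first infusion day. That is another population and covers all grades, but it gives no reason to expect many events at the second infusion. Premedication before each infusion, vital signs every 30 minutes and slowing or interruption for any reaction also apply.

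**Conclusion.** The contradiction is real and rests on complete running text in two parts of Section IV.ii. For a patient with a grade 3 infusion event on day 0, the protocol gives both 12 and 25 mL/h as the starting rate on day 14, a ratio of 2.08, with the dose unchanged. Two lesser defects go with it: a pointer in the wrong direction, and no statement of which table goes with a 12 mL/h start.

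This is an internal inconsistency in the administration instructions, worth correcting for safety. It is not a flaw in the statistical design: sample size, power, alpha and the primary endpoint are not affected. How many patients it would reach cannot be stated, because the documents give no rate of grade 3 infusion events in this population. The conclusion assumes that the set-up step is meant to be followed as written and that the grade 4 rule is applied. It implies no judgement on which starting rate is right.

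**What to change.** The sponsor should reconcile the subsequent-infusion paragraph with the set-up step, so that the same starting-rate instruction appears in both places. The text should state which rate table goes with each starting rate on day 14. The pointer in the set-up step should name the subsection where the rate rules stand. The choice of rate belongs to the sponsor and the clinical team.

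The cost is about one revised line, one table note and one corrected cross-reference in an amendment. Any local infusion instructions derived from the protocol would need to be brought into line. No extra procedures, data or patients are needed.
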